Division of Internal Medicine
Department of Vascular Diseases

[name]
[name]
T [name]
F [name]
E [contact]
W www.kclj.si

Date: January 26, 2019

Study Protocol and Statistical Analysis Plan

Arterial Function and Atherosclerosis in Patients With JAK2 V167F Positive Essential Thrombocythemia

Principal Investigator: [name], PhD,
Professor of Medicine,
Head, Department of Vascular Diseases

Funding: Project No. TP20180038, financed by the Fund for Tertiary Research and Development of the University Medical Centre Ljubljana

1. Overview and Aim of the Study

We will study patients with JAK2 V617F positive essential thrombocythemia (ET) without clinically apparent atherosclerotic vascular disease in comparison to age-and sex-matched, apparently healthy control subjects and measure changes in vascular function and morphology at baseline and after a 4-year observation period. In addition, the JAK2 V617F allele burden, i.e., the percentage of mutated alleles in leukocytes, will be determined and correlated with vascular function and morphology. The study protocol has been approved by the Committee for Medical Ethics of the Republic of Slovenia, approval number: 0120-428/2017/4.

Our aim is to test (a) whether changes in vascular function and morphology in a 4 year observation period differ between patients with JAK2 V617F positive ET in comparison with control subjects, and whether (b) the JAK2 V617F allele burden correlates with vascular function and morphology.

2. Patients and Control Subjects

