Patients with JAK2 V617F positive ET have been selected from the database of the Department of Hematology of the University Medical Centre Ljubljana, Slovenia, after having given their informed consent. Only patients without a personal history of clinically manifest atherosclerotic vascular disease (myocardial infarction, angina pectoris, peripheral arterial disease, aortic disease, transient ischemic attack or ischemic stroke) were eligible. The control group has been selected among apparently healthy employees of the University Medical Centre Ljubljana and their relatives. The groups have been matched for age and sex distribution and classical risk factors for cardiovascular disease. Forty patients (14 male and 26 female) with JAK2 V617F positive ET without clinically apparent cardiovascular disease were enrolled in the study in 2014 - 2015 for the first examination and 36 (12 male and 24 female) of them are expected to participate also in 2018-19. Forty two control subjects (16 male and 26 female) participated in the first examination in 2014-2015 and at least 38 (14 male and 24 female) subjects are expected to participate in the second examination.

Inclusion criteria for patients are: clinically confirmed ET with genetically confirmed JAK2 V617F mutation, age above 18 years, absence of clinically suspected or overt atherosclerotic vascular disease. For the control subjects, the inclusion criteria are being apparently healthy, matching the patients in age and sex, age above 18 years, and absence of clinically suspected or overt atherosclerotic vascular disease.

Exclusion criteria for both groups are: clinically suspected or overt atherosclerotic vascular disease, chronic kidney disease stage 3 and above, known cancer, chronic inflammatory disease, autoimmune disease, and pregnancy.

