All subjects will be examined twice, the first time in 2014 - 2015 and the second time in 2018 – 2019. All participants will have signed the informed consent form before enrolment. The subjects will complete a structured questionnaire about personal and family medical history, risk factors for cardiovascular disease and their medication. They will be physically examined and will donate blood samples for laboratory tests. Ultrasound examination of the extracranial carotid arteries will be done, and echo-tracking of the common carotid arterial wall will be used to assess the β-stiffness index and to estimate the pulse wave velocity. EndoPat plethysmography will be used to assess the endothelial function via the reactive hyperemia response of the digital arteries. Coronary artery calcium scanning will be performed to evaluate the extent of coronary artery calcification.

3. Baseline Measurements

Every participant will be examined physically, including measurements of height, weight, waist circumference, systolic and diastolic blood pressure. Blood will be taken for laboratory analyses - electrolytes, complete blood cell count, serum lipids, liver function tests, urea, creatinine, inflammatory markers and DNA

isolation for measurement of JAK V617F allele burden. A structured questionnaire about family history of cardiovascular diseases, personal medical history, smoking status and medications will be completed. The 10-year risk of coronary heart disease (CHD) and general cardiovascular disease (CVD) will be calculated using the Framingham risk equation.

4. Vascular Imaging

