Differences between subjects with ET and control subjects at the first and second examination will be tested by the chi-square test for discrete variables, for normally distributed continuous variables by the paired Student's t-test for independent samples, and for non-normally distributed continuous variables by the Mann-Whitney test for independent samples. P-values of < 0.05 will be considered significant with a correction for multiple comparisons.

Changes in vascular function and morphology in the 4-year observation period will be compared between the two groups by the log rank test. P-values of < 0.05 will be considered significant.

The association between the parameters of vascular function / morphology and the JAK2 V617F allele burden will be assessed by the Pearson correlation coefficient.

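### Aim (b) is analysed only by a crude allele-burden correlation; matching to controls does not control age among the ET patients, so an age-adjusted coefficient should be reported beside it

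*Combined protocol and SAP*

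**What the plan says.** Section 1 sets two aims. The second is to test whether "the JAK2 V617F allele burden correlates with vascular function and morphology".

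The whole analysis for that aim is the last sentence of section 7: "The association between the parameters of vascular function / morphology and the JAK2 V617F allele burden will be assessed by the Pearson correlation coefficient". Section 7 contains no partial correlation, regression or stratification.

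Age is handled in the design, in section 2: "The groups have been matched for age and sex distribution and classical risk factors for cardiovascular disease". Patients qualify with "clinically confirmed ET with genetically confirmed JAK2 V617F mutation, age above 18 years, absence of clinically suspected or overt atherosclerotic vascular disease". No upper age limit and no age distribution are given. On numbers, section 2 reports that "Forty patients (14 male and 26 female) with JAK2 V617F positive ET without clinically apparent cardiovascular disease were enrolled" and that "36 (12 male and 24 female) of them are expected to participate also in 2018-19".

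Section 3 adds a summary of cardiovascular risk: "The 10-year risk of coronary heart disease (CHD) and general cardiovascular disease (CVD) will be calculated using the Framingham risk equation". Neither age nor this score is carried into the correlation.

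Two further points bear on how the correlation is read:
- Section 6 measures allele burden in controls as well as patients, and section 7 does not name the sample for the correlation.
- The rule "P-values of < 0.05 will be considered significant" is attached in section 7 to the group comparisons and to the 4-year changes, not to the correlation.

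**The concern.** Matching patients to controls serves aim (a), the comparison of the two groups. Aim (b) is naturally a comparison among ET patients with higher and lower burden. Balance between patients and controls does nothing about age differences inside the patient group.

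If older patients tend both to carry a higher burden and to have worse arteries, a crude correlation appears even when burden adds nothing at a given age. If the two age relations run in opposite directions, age pushes the crude coefficient the other way and could hide an association that exists at a given age. In either case the crude coefficient cannot separate a link specific to the mutation burden from one that age produces.

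The plan treats age and classical risk factors as worth controlling for the group comparison, but makes no such provision for this aim.

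**Working it through.** The plan states no power, sample-size or effect-size figure for aim (b), so there is none to reproduce.

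**Inputs from the documents.** n = 40 patients at the first examination and 36 expected at the second (section 2).

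**Assumptions.**
- The correlation uses ET patients only.
- The test is two-sided at 0.05.
- Burden, vascular parameter and age are jointly Gaussian.
- Age is the only common cause, and there is no burden–artery link at a given age.
- The age correlations are assumed values, because the documents give none.

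**Step 1: expected crude correlation.** With age as the only link,

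r(burden, vascular) = r(age, burden) × r(age, vascular).

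For example, 0.3 × 0.6 = 0.18 and 0.4 × 0.6 = 0.24.

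**Step 2: chance that the crude test rejects zero.** By the Fisher z approximation this is Φ(√(n−3)·atanh r − 1.960) + Φ(−√(n−3)·atanh r − 1.960). At n = 40, √37 = 6.083.
- r = 0.18: atanh r = 0.182 and 6.083 × 0.182 = 1.107. Then Φ(−0.853) + Φ(−3.067) = 0.198.
- r = 0.24: atanh r = 0.245 and 6.083 × 0.245 = 1.489. Then Φ(−0.471) + Φ(−3.449) = 0.319.

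**Step 3: simulation check**, 40,000 data sets per cell:

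| r(age, burden) / r(age, vascular) | Expected crude r | Crude test rejects, n = 40 | Crude test rejects, n = 36 | Age-adjusted test rejects, n = 40 |
|---|---|---|---|---|
| 0 / 0.6 | 0 | 5.0% | 4.9% | 5.0% |
| 0.2 / 0.3 | 0.06 | 6.5% | 6.3% | 5.0% |
| 0.2 / 0.5 | 0.10 | 9.5% | 9.1% | 4.9% |
| 0.3 / 0.6 | 0.18 | 19.7% | 18.5% | 4.9% |
| 0.4 / 0.6 | 0.24 | 32.3% | 29.5% | 5.0% |
| 0.5 / 0.7 | 0.35 | 61.4% | 56.3% | 4.9% |

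The last row is an extreme case. Its expected r of 0.35 exceeds the critical value at both sample sizes (0.312 at n = 40, 0.329 at n = 36). The rates are per vascular parameter.

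**Step 4: price of adjusting for age.** The critical |r| is t/√(t² + df).
- n = 40, crude (df = 38): 2.024/√(4.098 + 38) = 0.312.
- n = 40, adjusted (df = 37): 2.026/√(4.106 + 37) = 0.316.
- At n = 36 it moves from 0.329 to 0.334.

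The correlation detectable with 80% power is tanh[(1.960 + 0.842)/√(n − 3 − k)], where k is the number of covariates. At n = 40 it moves from 0.431 to 0.436, and at n = 36 from 0.452 to 0.458.

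**The case against.** The strongest reply is that aim (b) asks only whether burden correlates with the vascular measures. A crude Pearson coefficient answers that literally. In the table, wherever the expected r is not zero, a true marginal correlation exists, and rejecting zero is a correct answer to the aim as worded. This stands. The percentages become error rates only if the aim is read as an association beyond age.

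A reader might also make four stronger inferences that the documents do not support:
- **That burden rises with age.** Nothing in the documents links the two, whether through clone growth, disease duration or treatment. If they are unrelated, age causes no bias.
- **That the enrolled patients span a wide age range.** Above 18 is an eligibility floor. No distribution is given, and the exclusions for atherosclerotic disease, cancer and chronic kidney disease could narrow the range.
- **That aim (b) would be declared met on p < 0.05.** Section 7 ties no threshold to the correlation.
- **That the correlation is confined to patients.** This is the natural reading, but it is inferred.

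The figures also rest on Gaussian data. They do not show how either coefficient behaves for a 0–6 plaque score or an Agatston score.

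What is left after these concessions is that the design does not control age among patients, the analysis does not adjust for it, and the crude coefficient alone cannot support a burden-specific conclusion.

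**Conclusion.** The point holds in conditional form, as a cheap improvement. The planned coefficient answers the literal wording of aim (b) and contradicts nothing in the plan. If burden and a vascular parameter are both related to age, though, it cannot show an association specific to the mutation burden, and the matching to controls does not help.

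The size cannot be fixed from the documents. Under the stated assumptions and n = 40, the crude test would reject in about 5% of cases (burden unrelated to age), 6.5% (0.2/0.3), 10% (0.2/0.5), 20% (0.3/0.6) or 32% (0.4/0.6), against about 5% after age adjustment. It would go too far to conclude that the planned analysis has an inflated false-positive rate as it stands. That needs both an age–burden relation, which the documents do not give, and an age-independent reading of the aim.

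**What to change.** In section 7, state that:
- within ET patients, the age-adjusted partial correlation (or regression coefficient) of each vascular parameter on allele burden will be reported beside the crude correlation;
- a burden-specific association will be concluded only from the adjusted result;
- a rank-based partial correlation will be used for any parameter that fails the plan's own normality test, for example the plaque score or the Agatston score if they fail it.

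This wording also settles the unnamed sample. It could at the same time say which examination's data are used, since that decides whether n is 40 or about 36.

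No new data are needed, because age is already required for eligibility and matching. The cost is one degree of freedom (critical |r| from 0.312 to 0.316 at n = 40) and an adjusted association that may be weaker than the crude one.
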